7.3. Data collection

Eligible participants identified from the CMP will be assigned a pseudonymous “study key”. The study key will be sent to the other participating organisations for linkage alongside the following direct identifiers:

- Date of birth
- NHS number
- Postcode
- Sex/gender

Linkage will be performed by each participating organisation, following the principles of the NHS Digital matching algorithm. At no point will direct identifiers be sent to the co-ordinating site (Critical Care Research Group, University of Oxford).

Participating organisations performing linkage will be:

- NHS Digital
- Patient Episode Database for Wales (PEDW)
- UK Renal Registry (UKRR)
- National Institute for Cardiovascular Outcomes Research (NICOR)
- Stroke Sentinel National Audit Programme (SSNAP)

On a per patient level, the study will request 5 years of diagnostic coding data prior to ICU admission (to accurately assess prior medical co-morbidities) and 1 year post hospital discharge (to assess the outcomes of this study).

After linkage, only pseudonymous personal data will be securely transferred to the sponsor (Critical Care Research Group, University of Oxford), where it will be stored and accessed within a secure computing system that conforms to UK government Cyber Essentials Plus and NHS Digital Security Toolkit certifications. The study will also link data from the UK Obstetric Surveillance System (UKOSS) to identify patients who were pregnant at the time of ICU admission. As UKOSS does not collect direct identifiers, it will be linked to the pseudonymous data set using probabilistic matching.

Data will be combined into the final pseudonymised study dataset by researchers in the Critical Care Research Group at the University of Oxford for analysis. Analysis of the study dataset will be conducted by researchers at the University of Oxford and ICNARC, following the methods outlined in Section 11. The accompanying Data Flow Diagram outlines the exchange of confidential patient information within the study.

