11. STATISTICS AND ANALYSIS

11.1. Statistical Analysis Plan (SAP)

The statistical aspects of the study are summarised here with details fully described in a statistical analysis plan that will be available from the time that the last participant is recruited. The SAP will be finalised before any analysis takes place.

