11.2. Description of the Statistical Methods

Primary outcome

The primary outcome will be all-cause mortality at 1 year after discharge from ICU. For patients transferred between ICUs, this will be the time of discharge from the last ICU. Dates of death will be extracted from Civil Registration (deaths).

Secondary outcomes

Secondary outcomes will be:

- All-cause mortality at 30, 60, 90 and 180 days
- Any emergency (non-elective) hospital admission
- Emergency hospital admissions for respiratory infection
- Emergency hospital admission for a venous thrombotic event (deep vein thrombosis or pulmonary embolism)
- Emergency hospital admission for a major adverse cardiac event (myocardial infarction, stroke, heart failure)
- Development of end stage renal failure treated by renal replacement therapy

Reasons for hospital admission (i.e. primary diagnosis) will be identified using the International Classification of Diseases 10th Edition (ICD- 10) codes obtained by linkage to the HES/PEDW. Where required, ICD-10 codes will be assigned to broader diagnostic groups (e.g. respiratory infections) as per the UK Summary Hospital-level Mortality Indicator (SHMI) (16).

Statistical methods

For patients treated on ICU for COVID-19 and comparator groups, we will report the unadjusted proportions/incidence of primary and secondary outcomes, along with cumulative incidence function estimates over the 1 year follow-up period. When considering secondary outcomes (and where appropriate), the cumulative incidence estimates will account for the competing risk of death. For the COVID-19 group, we will also investigate the effect of ICU admission time (i.e. early epidemic, late epidemic) as this may impact their outcomes, as treatments changed over time.

We will compare the risk of the primary and secondary outcomes between the COVID-19 and comparator groups using survival models, such as Cox proportional hazards regression models or Fine and Gray models (when death is a competing risk). We will fit both univariable models (i.e. just including the COVID-19 vs comparator group variable) and multivariable models including potential confounders.

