2.1. General study design and plan

This is a retrospective cohort study of outcomes for patients treated on an ICU in England and Wales, one year after discharge from hospital. Our primary group will include patients admitted to ICU with confirmed COVID-19 between 1st January and 1st July 2020, who were discharged alive from hospital. We will use the ICNARC Case Mix Programme (CMP) to identify comparator groups of emergency ICU admissions, to which outcomes in the primary group can be compared. Once identified, each cohort will be linked to the national data sets to obtain information on subsequent hospitalisations, and longer-term mortality, cardiac and renal outcomes.

The study will be reported using the REporting of studies Conducted using Observational Routinelycollected health Data (RECORD) (14).

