5.3.2. Secondary outcomes

Cause-specific readmissions will be identified by combining HES (ICD-10) and GDPPR coding, using coding sets defined in Ayoubkhani et al. (15). For a venous thrombotic event, we will include the following ICD-10 codes: I80.0-I80.3, I80.8-I80.9, I82.9, O22.2-O22.3, O87.0-O87.1, I26.0, and I26.9.

• Emergency hospital admission – any non-elective hospital admission. Recorded in the hospital episode statistics data set.

- Emergency hospital admission for respiratory infection any emergency hospital admission for a respiratory infection.
- Emergency hospital admission for a major adverse cardiac event (myocardial infarction, stroke, acute heart failure)
- Emergency hospital admission for a venous thrombotic event (deep vein thrombosis or pulmonary embolism)
- Development of end stage renal failure treated by renal replacement therapy

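### The SAP takes emergency admissions from HES (with GDPPR for cause) and never names PEDW, so, followed as written, it misses readmissions to Welsh hospitals and understates incidence

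*SAP*

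**What the plan says.** SAP 5.3.2 sets two source rules for the admission outcomes. Any emergency admission is "any non-elective hospital admission. Recorded in the hospital episode statistics data set". For the three outcomes tied to a cause (respiratory infection, major adverse cardiac event, venous thrombotic event), "Cause-specific readmissions will be identified by combining HES (ICD-10) and GDPPR coding". PEDW is not mentioned there or anywhere else in the SAP. The nearest general statement is in SAP 2.1, where "each cohort will be linked to the national data sets to obtain information on subsequent hospitalisations".

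The Protocol is wider. Section 11.2 takes the reasons for admission from ICD-10 "codes obtained by linkage to the HES/PEDW". Section 7.3 lists PEDW among the organisations that perform linkage, and section 12.1 lists it as a data source. Both keep it apart from NHS Digital, under which 12.1 places HES and the GPES pandemic planning data (GDPPR).

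Emergency admissions to adult general ICUs in either England or Wales are eligible (Protocol 8.2, SAP 4.1.1). Protocol 11.1 says that the statistical aspects are summarised in the Protocol, with "details fully described in a statistical analysis plan".

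**The concern.** SAP 5.3.2 is where the admission outcomes are defined in detail, and an analyst would code from it. It names a source, and that source does not appear to cover part of the eligible population. The Protocol treats HES and PEDW as different databases, and a title in its own reference list (reference 14) describes HES as English hospital administrative data.

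In routine data, a patient with no matching admission record looks the same as a patient who was not readmitted. Patients from Welsh ICUs would therefore remain in the denominator with most of their readmissions invisible. Four of the five secondary outcomes are emergency admissions. Estimating these risks is a stated secondary objective (SAP 1.2), and SAP 5.4.1 tabulates the number and proportion with each event in each cohort. A downward bias in those proportions does not shrink with sample size, and adjusting for region cannot restore events that were never captured.

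**Working it through.** **1. The texts side by side**

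| Item | Protocol | SAP |
|---|---|---|
| Eligible ICUs | England or Wales (8.2) | England or Wales (4.1.1) |
| Any emergency admission | No source in the outcome list (11.2); HES and PEDW both linked (7.3, 12.1) | HES (5.3.2) |
| Cause of admission | HES/PEDW (11.2) | HES plus GDPPR (5.3.2) |
| PEDW named | Yes (7.3, 11.2, 12.1) | No |

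The HES/PEDW wording in Protocol 11.2 concerns reasons for admission. For the any-admission outcome, the mismatch is with the source lists in 7.3 and 12.1.

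**2. The population**

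The stated total reproduces: 90,000 × 3.5 + 4,600 = 319,600, for England and Wales combined (Protocol 11.3, SAP 2.2). Neither document divides it by country, so the Welsh share must be assumed.

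**3. Effect on incidence**

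Let w be the share of the cohort from Welsh ICUs, and e the fraction of their readmissions that occur in England and so still reach HES. Take the readmission risk as the same in both countries. Then:

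- observed incidence = true incidence × [1 − w(1 − e)]
- relative understatement = w(1 − e)

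With w assumed at 2-8% and e at 0-20%:

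- smallest: 0.02 × 0.8 = 1.6%
- largest: 0.08 × 1.0 = 8%

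At an assumed true 1-year risk of 30%:

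- observed 30 × 0.984 = 29.5% down to 30 × 0.92 = 27.6%, so 0.5 to 2.4 percentage points too low
- COVID-19 cohort: 4,600 × 0.30 = 1,380 patients with an event, of whom 1,380 × 0.016 = 22 to 1,380 × 0.08 = 110 would be missed

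At an assumed risk of 5%, the shortfall is 5 × 0.016 = 0.08 to 5 × 0.08 = 0.40 points.

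**4. Effect on comparisons**

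With e = 0, the crude risk ratio is multiplied by (1 − w in COVID-19) / (1 − w in comparator).

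- Equal shares: factor 1
- 3% COVID-19 against 5% comparator: 0.97 / 0.95 = 1.02
- 8% against 3%: 0.92 / 0.97 = 0.95

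For the cause-specific Cox hazard ratio, I computed the large-sample value when Welsh patients are at risk but never show the event. Assumptions: e = 0; 1-year risk 5% or 30%; true hazard ratio 0.8, 1.0 or 1.3; death hazard 0.12 per year in both groups; equal shares of 2-8%; comparator 1 or 68 times the size of the COVID-19 cohort. The ratio of observed to true hazard ratio lay between 0.9946 and 1.0035, a shift of about 0.5% at most. With unequal shares, at 30% risk and a true hazard ratio of 1.0, the observed value was 0.94 for 8% against 3% and 1.08 for 2% against 8%.

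**The case against.** The strongest reply is that silence is not exclusion. The SAP also never names UKRR, NICOR, SSNAP or UKOSS, and nobody would conclude that those linkages were dropped. The Protocol itself uses HES as shorthand: section 8.3 refers only to HES and audit databases when discussing registration delay for the whole cohort (repeated in SAP 4.1.2), and section 13.1 omits PEDW when describing where follow-up data are held. SAP 2.1 promises linkage to national data sets in general terms. On this reading SAP 5.3.2 is loosely drafted, and PEDW would be used in practice.

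Most of that stands. Loose drafting is the likelier explanation, and a reader who infers a decision to discard Welsh admissions goes further than the documents allow. It does not remove the point, because for admissions SAP 5.3.2 is not silent: it names a source, and a specific outcome definition takes precedence over a general remark about linkage.

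It is also fair to say that the size rests wholly on assumptions, and that in the COVID-19 cohort sampling error may be larger. At 30% risk and n = 4,600 the 95% half-width is 1.96 × √(0.30 × 0.70 / 4,600) = 1.32 points. The bias exceeds this only if the Welsh share is above 1.32 / 30 = 4.4%, or 4.4 / 0.8 = 5.5% with 20% captured in England.

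A reader might also infer that SAP 5.3.2 abandons the Protocol's primary-diagnosis rule, or lets a GDPPR code count as an event without an admission. The documents do not support either. Not repeating a rule does not contradict it. Each cause-specific outcome is already worded as an emergency hospital admission. The cited coding sets, which may settle code position, are not available here.

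**Conclusion.** The point holds as a defect in a stated source rule. Applied literally, SAP 5.3.2 leaves out readmissions to Welsh hospitals for an England-and-Wales cohort and understates the absolute incidence of four of the five secondary outcomes. The relative understatement is about the Welsh share less whatever is captured in England: 1.6-8% for assumed shares of 2-8% and 0-20% captured. The documents give neither quantity, so this is an illustration and not an estimate.

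It would be tempting to conclude that the main comparisons are compromised, but the documents do not support that. Death comes from civil registration and is untouched. Hazard ratios barely move if Welsh shares are equal. Region is among the covariates in SAP 5.2 for the propensity score and the multivariable models, which limits the effect of unequal shares there. The unadjusted comparisons in SAP 5.4.2 have no such protection, but nothing in the documents shows that the shares differ. Secondary outcomes carry no p-values (SAP 3.1). This is a minor to moderate point: it should be corrected because the correction is cheap, and it does not threaten the primary result.

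**What to change.** In SAP 5.3.2, define every admission outcome as a non-elective admission recorded in HES Admitted Patient Care or PEDW. Add that GDPPR, which the Protocol lists under NHS Digital, supplements the coding only where it is available. This is a change of wording only, since PEDW linkage is already planned.

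If PEDW data are not obtained, restrict the admission outcomes, in both numerator and denominator, to patients of English ICUs, and report this as a deviation under SAP 3.3. The cost of that fallback is that Welsh patients are lost from the admission outcomes, though not from mortality. Readmissions to Welsh hospitals among patients of English ICUs would still be missed, and the report should say so.

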5.4. Analysis methods

5.4.1. Descriptive analysis of incidence

The incidence of each of the primary and secondary outcomes will be summarised within each cohort. Kaplan-Meier curves will be used to graphically display the number of patients who die in the follow-up period, whilst cumulative incidence function curves will be used to display all of the secondary outcomes (treating death as a competing risk). The number and proportion of patients experiencing each event will be tabulated at each of the outcome assessment time points. Further analyses will investigate the event rates within relevant subgroups (described in Section 5.5). For continuous variables (such as age) we will additionally consider regression modelling with non-linear terms (e.g. fractional polynomials or restricted cubic splines) to describe the impact of the variable on the patient's risk of experiencing the outcome events.

5.4.2. Comparison of COVID-19 cohort to other cohorts using standard regression modelling

To compare the risk of the primary outcome (death) between the COVID-19 cohort and the other cohorts, we will use Cox proportional hazards regression models to estimate the hazard ratio (and 95% confidence interval). The hazard ratio (HR) will be calculated at each of the outcome assessment time points. For the secondary outcomes, a competing risk approaches will be used, with death as the competing risk. We will use the cause-specific Cox proportional hazards regression approach to estimate the cause-specific hazard ratio (and associated 95% confidence interval). The Fine-and-Gray approach will be used as a sensitivity analysis to estimate the sub-distribution hazard ratio. For each of these analyses we will report unadjusted results.

5.4.3. Comparison of COVID-19 cohort to other cohorts using propensity score matching

For each comparison of the COVID-19 cohort to a non-COVID cohort we will use propensity score matching to create cohorts that are similar in terms of baseline characteristics and confounding variables. We will construct a propensity score using logistic regression where the outcome is the cohort status, and the covariates will be those previously defined in Section 5.2. The model will allow for non-linear relationships between continuous variables and the outcome. The propensity score will then be estimated for each patient. One to one matching will be performed based on the

propensity score, initially using a nearest neighbour (greedy) approach. We will assess the balance achieved through the matching process using standard approaches, such as Q-Q plots, and assessments of the absolute standardised mean difference. If the covariates are not well balanced after nearest neighbour matching, alternative approaches will be tested, such as full matching, until sufficient balance is achieved. If sufficient balance cannot be achieved or too many patients from the COVID cohort are removed by the matching algorithm, we will consider using the propensity score for inverse probability weighting in our Cox regression models.

Once matched cohorts have been identified, we will analyse the outcomes with the standard regression modelling as described in Section 5.4.2– using Cox regression for the death outcome, and competing risk approaches for the secondary outcomes. However, since the data will now be clustered due to the matching, we will need to account for this in the regression models. We will therefore use cluster-robust standard errors.

5.5. Subgroup analyses

For both the unadjusted and propensity-matched analyses, we will investigate the following subgroups: age, sex, ethnicity and length of advanced organ support.

5.6. Sensitivity analyses

To assess the robustness of the propensity-matched analysis, we will also fit multivariable regression models. We will use restricted cubic splines or fractional polynomials to allow for potentially nonlinear relationships between continuous covariates and outcomes. The adjustment variables will be those listed in Section 5.2.

5.7. Missing data

The proportion of missing data for each of the outcome measures and variables of interest will be described. In addition, we will describe the patterns of missingness.

We anticipate that missing data will be minimal, in which case we will use a complete case analysis, i.e. omitting any patients with missing data. However, if the amount of missing data is relatively high (more than 5% of patients have missing data) we will use multiple imputation. In this case we would also perform a complete case analysis as a sensitivity analysis.

5.8. Statistical software

It is expected that all analysis will be carried out using R statistical software.

6. Conclusion

The intention of this study is to understand the long-term consequences of being admitted to ICU with COVID-19. Initially analyses will be descriptive in nature. We will then go on to summarise whether these long-term consequences are different from those that are associated with admission to ICU for other causes. We will use different comparison cohorts and different analysis methods to check the robustness of our conclusions.

This statistical analysis plan presents the principles of the analysis that we intend to follow in the OPTIC-19 study. We hope that by pre-specifying our analyses we will minimise the risk of reporting bias and data driven results.

7. References

- 1. World Health Organization. Coronavirus disease (COVID-19) Situation Report 183. 2020.
- 4. Intensive Care National Audit and Research Centre (ICNARC). ICNARC report on COVID-19 in critical care (17th July 2020). 2020;
- 6. Bion J. Long-term survival after intensive care. BMJ [Internet]. 1990 Dec 8;301(6764):1336– 1336. Available from: http://www.bmj.com/cgi/doi/10.1136/bmj.301.6764.1336
